### **3.0 Inclusion and Exclusion Criteria**

#### **3.1 Screening for eligibility.**

##### **A. Recruitment**

We will randomize approximately 374 participants over approximately 36-months, allowing for a conservative 20% dropout to allow for uncertainties in the post-COVID-19 environment. We will identify participants using 1) inpatient admission list, 2) referral from providers, 3) CR consults list, and 4) approved flyers, letters, and mailings, 5) cardiology consult lists and clinics, and 6) discharge list

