## Study Timeline

## 6.0 Study Endpoints

### 6.1 Primary and secondary study endpoints.

All eligible and consenting patients will undergo a standard battery of assessments at baseline and after approximately 3, 6, and 12 months (12 months as the study length allows). Assessors will be blinded regarding each patient's group assignment.

Aim 1: to test relative benefits of the MACRO vs. SOC arms, comparing (a) differences in the AM-PAC CAT Basic Mobility Domain (primary outcome; primary endpoint 3 months), as well as (b) complementary functional/qualitative metrics accelerometry, AM-PAC CAT Daily Activity Scale, depression, frailty, self-efficacy, and quality of life; (c) differences in participation, and adherence; (d) readmissions and hospitalization.

[figure not shown]
In Aim 2, assessments in physical activity (accelerometry); AM-PAC CAT Daily Activity Domain; depression; frailty; self-efficacy; and quality of life will be repeated at approximately 6 and 12 months (12 months as the study length allows) to evaluate longer term impact of the MACRO intervention vs. SOC.

In Aim 3, moderator analyses will examine characteristics of patients to identify those most likely to benefit from a MACRO intervention.

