C. **Statistical Analyses.** Overview-We will perform all main analysis based on intention-to-treat philosophy following the a priori plans outlined below. All statistical analyses will be performed and overseen by the study statistician [name] using SAS® version 9 (SAS Institute, Inc., Cary, North Carolina). Participant flow will be summarized using a CONSORT diagram. Data will be summarized by treatment group and time point as well as baseline to follow-up change using appropriate descriptive statistics. First, the baseline participant characteristics will be compared between the two arms. Any significant differences will be noted and accounted for as additional covariates in the sensitivity analyses. Second, main analyses to address the aims will be performed as outlined below. Confirmatory hypothesis testing will be performed using multiple imputation for missing data. Third, a set of sensitivity analyses including additional covariates and ignoring missing data will be performed to evaluate the robustness of our findings.

**Baseline Comparisons**-Due to the randomization scheme balanced with respect to study site and the large sample size, it is unlikely that other baseline participant characteristics will be significantly different between the arms. However, we will control for any participant characteristics that are found to be significantly different by including them as additional covariates in the sensitivity analyses. In such an event, we will not alter the primary analytic strategy to preserve its a priori nature and predictability. We will use independent samples *t*-, Wilcoxon rank sum, chi-square and Fisher's exact tests, as appropriate based on distributional properties, and continuous/categorical nature of the characteristic being compared.

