**Aim 1 Analysis**-We will fit a series of linear mixed models using the SAS® MIXED procedure with baseline to follow-up changes in continuous outcomes as the dependent variable; intervention arm (MACRO/SOC), follow-up time point (3/6/12 months) and their interaction term as the fixed effects of interest; the baseline value of the continuous outcome as a fixed effect covariate; and a participant random effect to account for multiple measurements over time from the same participant. We will appropriately construct means contrasts to estimate MACRO vs SOC at each follow-up time point. The magnitude and statistical significance at  $\alpha=0.05$  of the MACRO vs SOC difference at 3 months for AM-PAC CAT Basic Mobility Domain will serve as the formal test of the primary hypothesis H1.1. If significant, we will define a meaningful responder as having at least a 2.60 point improvement in AM-PAC CAT Basic Mobility Domain over 3 months, compute percentage of responders in both arms, and conclude a number-needed-to-treat (NNT) as the reciprocal of the difference in percentages. We will employ the same analytic strategy described above for each of our secondary continuous outcomes such as physical activity, depression, frailty, self-efficacy and quality of life (H1.2). For the secondary outcomes measured only once at 3 months such as participation, adherence and satisfaction (H1.3), we will consider using Wilcoxon rank sum, chi-square and Fisher's exact tests to make between-intervention comparisons, depending on the categorical/ordinal/interval nature of the outcomes and their propensity for ill-behaved distributional properties. For count outcomes such as falls, number of medications, readmissions and hospitalizations in H1.4, we will fit a series of negative binomial regression models with the count outcome as the dependent variable; exposure time for the counts as an offset; a log link function; and intervention arm as the main independent factor of interest; and a marker of history of the outcome at baseline as a covariate MACRO vs SOC incident rate ratio and its statistical significance will serve as tests of H1.4.

**Aim 2 Analysis**-In the linear mixed models described above for H1.1 and H1.2, we will examine the between-intervention means contrasts at 6- and 12-months. The magnitude and statistical significance of the MACRO vs SOC arm differences at 6 and 12 months will serve as the formal test of the hypothesis H2.1.

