**Missing Data**-The best approach for handling missing data is prevention, and our clinical trials have had a low missingness rate. We will clearly document missing data and reasons in the CONSORT diagram and compare those with missing data to complete data at the follow-up assessments using the same methods outlined under *Baseline Comparisons* subsection above. We will use methods such as multiple imputation which consider the uncertainty involved in imputing missing data. Multiple imputation is arguably the best method to account for missing data under the ignorable or missing-at-random (MAR) assumption, and mitigates bias even when missing data is non-ignorable. Specifically, we will generate M=5 imputed values for each missing value, analyze the 5 datasets as though complete, and finally combine the results appropriately so that they reflect the uncertainty involved in imputation. SAS® MI and MIANALYZE procedures will be used. Other approaches to missing data will also be considered in sensitivity analyses.

**Sensitivity Analyses**-We will perform sensitivity analyses to examine the robustness of our results against various assumptions, such as fitting zero-inflated models or using dichotomous (any/none) operational definitions and logistic regression models. In addition, if analyses of residuals from the linear mixed models show violations of statistical assumptions, we will consider fitting models after Box-Cox transforming the continuous variables to make them approximately conform to a normal distribution.

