#### D. Sample Size and Power.

**Sample Size Justification.** We base our sample size on published data, published statistical methods, and commercially available software (SAS® POWER procedure; SAS Institute, Inc., Cary, North Carolina). Between-subject standard deviation of the baseline to follow-up change in the primary outcome AM-PAC CAT Basic Mobility Scale is approximately 7.97 in rehabilitation outpatients. We consider 2.60 points a minimally clinically important difference based on MDC68. We plan to randomize 187+187=374 participants, anticipating 149+149 completers assuming a conservative 80% retention rate. We can detect a between treatment arm difference of 2.60 points in AM-PAC CAT Basic Mobility Scale with 80% statistical power in a two-tailed test at  $\alpha=0.05$ . This difference is smaller than the actual observed changes previously reported, indicating ample statistical sensitivity. The logistic regression model proposed in Aim 3 requires a minimum of about 5-10 events per variable, and assuming a half in the MACRO group responds, we would be able to fit a multivariable model with at least 15 variables. Thus, we are confident of the adequacy of sample size to address all aims.

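### The confirmatory test of H1.1 uses only five imputations: valid, but a larger M would remove avoidable noise near p = 0.05 and, at 20% missing, recover 2 to 3 points of power

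*Combined protocol and SAP*

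**What the plan says.** All references are to the combined protocol and SAP.

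- **Section 9.1 C, Overview:** "Confirmatory hypothesis testing will be performed using multiple imputation for missing data". An analysis that ignores the missing data is kept as a sensitivity analysis.
- **Section 9.1 C, Aim 1 Analysis:** the size and significance, at alpha 0.05, of the 3-month difference between arms in AM-PAC CAT Basic Mobility "will serve as the formal test of the primary hypothesis H1.1". The responder and number-needed-to-treat calculation follows only if that test is significant.
- **Section 9.1 C, Missing Data:** "we will generate M=5 imputed values for each missing value, analyze the 5 datasets as though complete". On software it says that the SAS "MI and MIANALYZE procedures will be used". It assumes data missing at random and reports low missingness in the team's earlier trials. It gives no seed, PROC MI method or list of imputation variables, and does not say whether arms are imputed together or separately.
- **Section 9.1 D:** the sample size rests on 187 per arm, "anticipating 149+149 completers assuming a conservative 80% retention rate", and then states: "We can detect a between treatment arm difference of 2.60 points in AM-PAC CAT Basic Mobility Scale with 80% statistical power".
- **Timing of the 20% loss:** section 3.1 A describes "allowing for a conservative 20% dropout to allow for uncertainties", and section 17.0 places the 20% at the 52-week follow-up. Section 6.1 puts the primary test earlier: "primary outcome; primary endpoint 3 months".

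**The concern.** Multiple imputation is a random procedure. Rubin's rules allow for a small number of imputations, so the test keeps its size. They do so by widening the interval and reducing the degrees of freedom, which costs power, and the estimate still moves from one set of random draws to the next. Here that random component sits inside the single test that decides the primary hypothesis and opens the responder analysis.

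Two things are at stake. First, if the result is borderline, running the same planned analysis with another seed can reverse the verdict. Because neither seed nor imputation model is stated, nobody could repeat the result from the plan or show that the seed was not chosen after the fact. Second, the 80% power in section 9.1 D belongs to an analysis of 149+149 completers, not to the M=5 procedure that will be run. Both costs can be avoided at almost no expense.

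**Working it through.** **Inputs from the plan.** 187 randomised and 149 completers per arm, SD of change 7.97, difference 2.60, two-sided alpha 0.05 (section 9.1 D); M=5 (section 9.1 C).

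**Assumed inputs (no figure in the plan).** Share missing at 3 months: 5, 10, 15 or 20%. Correlation r of baseline with change: 0, -0.3 or -0.5. Loss is equal in both arms and imputation uses arm and baseline only, so the fraction of missing information f equals the missing share.

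**Step 1. The plan's own power.** SE = 7.97 × √(2/149) = 0.923. Power = Φ(2.60/0.923 − 1.96) = 80.4% (80.1% by noncentral t). The stated 80% is reproduced, as a completer analysis.

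**Step 2. The M=5 test at 20% missing, r = 0.**
- Complete-data variance U = 7.97² × 2/187 = 0.679.
- Between-imputation variance B = U × f/(1−f) = 0.679 × 0.25 = 0.170.
- Total variance T = U + (1 + 1/M)B. With M=5, T = 0.679 + 1.2 × 0.170 = 0.883 and SE = 0.940. With M=100, SE = 0.922.
- Rubin degrees of freedom with M=5: 4 × (1 + 0.8/(1.2 × 0.2))² = 75.1.
- Noncentrality = 2.60/0.940 = 2.77. The noncentral t then gives power of about 78.0%, against 80.6% for unlimited M.

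**Step 3. Simulation.** Rubin's rules with Barnard-Rubin degrees of freedom, 300,000 draws with two independent seeds per cell, r = 0. Disagreement means that one seed gives p < 0.05 and the other does not.

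| Missing at 3 months | Power lost, M=5 v M=100 (points) | Disagreement M=5 | M=20 | M=50 | M=100 |
|---|---|---|---|---|---|
| 20% | 2.8 (77.3% v 80.1%) | 9.4% | 3.9% | 2.4% | 1.7% |
| 10% | 1.1 | 4.7% | 2.1% | 1.3% | 0.9% |
| 5% | 0.4 | 2.8% | 1.3% | 0.8% | 0.6% |

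At 20% missing, power is 79.6% with M=20 and 80.0% with M=50. With no true effect, type I error is 5.0-5.1% in every cell.

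**Step 4. Baseline adjustment, 20% missing.** At r = -0.3 power is 81.1% v 83.6% (M=5 v M=100) and M=5 disagreement is 8.5%. At r = -0.5 power is 87.9% v 90.2% and disagreement is 6.3%. The level rises, but the loss stays at 2.6 and 2.3 points.

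**Step 5. Data-level checks.** A separate simulation with imputation within arm (200,000 trials, r = 0) gave these powers for M=5 v M=100:

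| Missing | M=5 | M=100 |
|---|---|---|
| 20% | 77.5% | 80.4% |
| 15% | 80.9% | 82.7% |
| 10% | 83.7% | 84.8% |
| 5% | 86.3% | 86.7% |

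Another, with Bayesian regression imputation followed by ANCOVA, gave 77.3% v 79.9% at 20% missing.

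**Step 6. Where verdicts flip.** The seed-to-seed SD of the estimate, as a share of its SE, is √(f/M). At 20% missing this is 0.20 for M=5 and 0.045 for M=100. A data set whose large-M p is 0.05 then gives p from 0.020 to 0.137 with M=5 (5th to 95th percentile over seeds), against 0.041 to 0.062 with M=100. If the large-M p is 0.03, about 30% of M=5 seeds give p > 0.05; none of 1,500 did with M=100. Grouped by complete-case p at 20% missing, two M=5 seeds disagree in 39-40% of data sets at p = 0.02-0.05 and 36-37% at 0.05-0.10. They disagree in about 15% at 0.01-0.02 and only 0.1-0.2% below 0.005.

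**The case against.** The strongest reply is that nothing here is an error. M=5 is valid, the plan runs the test once, and clear results do not change. The 20% is described as conservative and tied to 52 weeks, and the team reports low missingness in its earlier trials, so loss at 3 months is probably smaller. At 5-15% missing, M=5 power is still above 80% even with r = 0. Since the primary model adjusts for baseline, r = 0 is itself pessimistic; at r = -0.3 the M=5 test keeps 81.1% power even at 20% missing. If patients missing at 3 months return later and those visits enter the imputation (assumed correlations 0.4-0.6), the loss falls to 1.4-2.1 points. The sensitivity analysis that ignores missing data would provide a seed-free result to read beside a borderline one. And a seed is often fixed in program code rather than in a protocol.

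Most of this stands, and it limits the size of the point. It does not remove it. Section 9.1 D uses 80% retention for the primary power statement, so 20% missing is the plan's own planning case. The sensitivity analysis does not decide H1.1. At every missing share and correlation examined, M=5 loses some power and adds seed noise that a larger M would remove; at 5-10% missing, disagreement is still more than four times that of M=100. The silence on seed and imputation model would, alone, be only missing detail. The choice of M carries the point.

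**Conclusion.** The concern holds as an efficiency and repeatability point, not a validity error. At the plan's 20% loss, M=5 costs 2.3-2.8 points of power across the correlations examined. That takes power below the planned 80% only if baseline adjustment gains nothing. Two seeds disagree on significance in 6.3-9.4% of trials. At 10% missing the cost is 0.7-1.1 points with 2.7-4.7% disagreement; at 5% it is 0.2-0.4 points with 1.5-2.8%. Almost all of the risk falls on results with p roughly between 0.01 and 0.10.

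These sizes rest on equal loss in both arms, imputation from arm and baseline only, and a 3-month contrast that behaves like a single-visit ANCOVA. The missing shares at 3 months and the baseline correlations are assumptions. The 20% is a cautious planning figure rather than a strict upper bound.

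**What to change.** In section 9.1 C, Missing Data, replace M=5 with a larger fixed number, for example M=50-100. M=20 already recovers most of the power; going to 50-100 is for repeatability.

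In the same place, state:
- the PROC MI seed;
- the PROC MI method;
- the imputation variables, for example arm, site, baseline and the 3-, 6- and 12-month Basic Mobility values;
- whether arms are imputed together or separately.

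Only the larger M reduces the noise. The seed and model make the result repeatable and rule out choosing a seed afterwards.

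The cost is one or two sentences of SAP wording and minutes of computing. The design, sample size, data collection and primary model do not change.

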#### D. Sample Size and Power.

**Sample Size Justification.** We base our sample size on published data, published statistical methods, and commercially available software (SAS® POWER procedure; SAS Institute, Inc., Cary, North Carolina). Between-subject standard deviation of the baseline to follow-up change in the primary outcome AM-PAC CAT Basic Mobility Scale is approximately 7.97 in rehabilitation outpatients. We consider 2.60 points a minimally clinically important difference based on MDC68. We plan to randomize 187+187=374 participants, anticipating 149+149 completers assuming a conservative 80% retention rate. We can detect a between treatment arm difference of 2.60 points in AM-PAC CAT Basic Mobility Scale with 80% statistical power in a two-tailed test at  $\alpha=0.05$ . This difference is smaller than the actual observed changes previously reported, indicating ample statistical sensitivity. The logistic regression model proposed in Aim 3 requires a minimum of about 5-10 events per variable, and assuming a half in the MACRO group responds, we would be able to fit a multivariable model with at least 15 variables. Thus, we are confident of the adequacy of sample size to address all aims.

#### 9.2 Steps to secure data to maintain confidentiality during storage, use, and transmission.

All research staff must complete training in protection of subject privacy and prevention of disclosure of identifying information.

All data collection forms are maintained in a secure office space.

Our study databases are maintained in locked computer files or on secure hard drives that are password protected; to which only authorized staff have access. A study manager must provide permission for programmers and research assistants to access study databases.

A study identification number will be assigned to each participant. This identification number will be randomly generated and will only be connected to patient identifiers by a master list maintained at each site.

### **9.3 *Describe any procedures that will be used for quality control of collected data.***

**Quality Control.** All study staff will undergo certification training prior to the beginning of the study. Every month data checks will occur to check accuracy of the data collection. Additionally, to ensure uniformity of sites there may be site visits and on-site trainings for staff.

## **10.0 *Provisions to Monitor the Data to Ensure the Safety of Subjects***

Serious adverse events (SAE) and Adverse events (AE) will be reported to the DSMB following the DSMB charter guidelines. The DSMB will have the ability to stop the study at any time if there are concerns about safety. SAE will also be reported to each active site's IRB following the provisions required for that site.

- To provide for more complete assessment of the possible impact of COVID-19 on MACRO, the unblinded study physician and study coordinator at each site will work immediately and directly with the study statistician if they have any concerns that an AE/SAE is attributable to COVID-19. This will prompt an expedited report to the DSMB and NIA.

The AE/SAE SOP will be updated accordingly.

## **11.0 *Withdrawal of Subjects***

Participants may withdraw from the research at any time. If participants decide to leave the research, they should contact the site PI at their active site.

If participants stop being in the research, data already collected may not be removed from the study database. Participant will be asked whether the investigator can collect data from their routine medical care. If the subject agrees, this data will be handled the same as research data.

## **12.0 *Risks to Subjects***

### **12.1 *Foreseeable risks***

#### **A. *Risks associated with the MACRO home-based and hybrid-based CR program.***

Participants will be increasing exercise and physical activity. Such activity may be associated with muscle soreness, musculoskeletal irritation, shortness of breath, fatigue, light-headedness, chest discomfort, or nausea. Physical activity and exercise may also be associated with an increased risk of a cardiovascular event, such as a heart attack, cardiac arrest, dangerous arrhythmia, or stroke. However, MACRO participants will always be approved for participation by their personal clinician to best ensure they are sufficiently stable and such that risks are minimized.

Participants participating in CR (site- hybrid, or home-based models) will not participate in progressive exercise until a physician deems it appropriate.

**B. MACRO intervention**

CDC CHECK FOR SAFETY; A Home Fall Prevention Checklist for Older Adults will be mailed to participants and education will be provided based on participant questions. If there are concerns raised by this the PCP will be contacted and a clinical safety assessment will be requested on the participants behalf.

**C. Cognitive and depression assessment.** The PHQ9 and Short Blessed (screening) assessments. Each assessment will be self-completed by participants, and they will have the option to skip questions if they feel uncomfortable answering. Additionally, staff will be trained in addressing questions and will have direct contact with clinical staff to handle more complex occurrences following each hospitals outpatient standard operation procedures for increased behavioral health assistance.

**D. Risks associated with questionnaire administration.** Participation includes a risk of loss of confidentiality regarding personal health information. However, all research staff have undergone formal human subjects training to reduce this risk. Research staff are trained to protect the privacy of research subject participants. Burdens associated with questionnaires may be exacerbated by the challenge of administering these tools over the phone.

**E. Accelerometry assessment:** Participants may wear an ActiGraph which is a watch like device that goes on your wrist for 7-10 days there is the small chance it may cause a rash or irritation of the skin but no more than wearing a regular watch.

**12.2 If applicable, indicate which procedures may have risks to the subjects that are currently unforeseeable.**

There may be risks that are currently not foreseeable as part of the study assessment and intervention.

